10.2 Laboratory Tests

Descriptive statistics of the observed values and change from baseline (continuous data) will be presented for each haematology (*Table 14.3.4.1*) and chemistry (*Table 14.3.4.2*) parameter by visit.

Shift tables will display numbers of participants with normal range shifts at baseline versus post-treatment at Day 2, Week 4, and Week 12 (*Table 14.3.4.3* and *Table 14.3.4.4* for haematology and chemistry, respectively).

Listings for haematology, chemistry, and urinalysis data (*Listing 16.2.8.1*, *Listing 16.2.8.2*, and *Listing 16.2.8.3*) will also flag values that are outside normal reference ranges or markedly abnormal findings. Clinically significant laboratory data will also be listed separately (*Listing 16.2.8.4*).

10.3 Vital Signs

Descriptive statistics of the observed values and change from baseline on non-administration and administration visits will be presented for each parameter by visit and by timepoint on COMP360 administration day (*Table 14.3.5.1*, *Figure 14.3.5.1* [for day of dosing only]). Individual participant plots will also be produced for the observed and change from baseline values for each parameter by timepoint on COMP360 administration

day only (*Figure 14.3.5.2*). The number and percentage of participants with values outside clinically important limits, as described in Section 8.3.3.1 will be summarised by visit and timepoint on COMP360 administration day (*Table 14.3.5.2*).

All vital signs data will be listed, which will also include flagged values that are outside normal reference ranges or markedly abnormal findings (*Listing 16.2.8.7*). Clinically important vital signs values will also be listed separately (*Listing 16.2.8.8*).

10.4 ECGs

Descriptive statistics of the observed values and change from baseline will be presented for each parameter by visit (*Table 14.3.6.1*).

Shift tables in relation to the overall interpretation (normal, abnormal not clinically significant (NCS), and abnormal clinically significant (CS) at baseline versus post-COMP360 administration at Day 2 will be presented (*Table 14.3.6.2*).

The number and percentage of participants meeting the QTc intervals as described in Section 8.3.4.1 will be summarised by visit (*Table 14.3.6.3*).

All ECG data will be listed (*Listing 16.2.8.9*). Clinically important ECG values will also be listed separately (*Listing 16.2.8.10*)

10.5 C-SSRS

C-SSRS data will be summarised by visit (*Table 14.3.6.4*) and listed (*Listing 16.2.9.2*).

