8.2 Safety Assessments

8.2.1 *Columbia-Suicide Severity Rating Scale*

The C-SSRS will be used to assess suicide potential or tendency as a study entry criterion and monitored throughout the study.

The C-SSRS is a semi-structured interview designed to assess the severity and intensity of suicidal ideation, suicidal behaviour, and non-suicidal self-injurious behaviour over a specified time period. The measurement of suicidal ideation is based on five “yes” or “no” questions with accompanying descriptions arranged in order of increasing severity. If the patient answers “yes” to either questions 1 or 2, the intensity of ideation is assessed in five additional questions related to frequency, duration, controllability, deterrents, and reasons for the most severe suicidal ideation. Suicidal behaviour is assessed by asking questions categorising behaviours into actual, aborted, and interrupted attempts; preparatory behaviour; and non-suicidal self-injurious behaviour.

If any item(s) on the C-SSRS are answered “yes”, the primary investigator or physician investigator must review the patient's responses in order to (a) at screening and day-1 determine the patient's study eligibility and potential need for referral to a mental health professional, and (b) during the study evaluate the patient's need for appropriate medical management such as a referral to a mental health professional.

A significant risk of suicide is defined as a “yes” in answer to (a) questions 4 or 5 on the suicidal ideation section; or (b) any questions on any item in the suicidal behaviour section. This must be reported as an AE or SAE as appropriate and followed up accordingly. Additionally, if a patient responds “yes” to any of the suicidal ideation questions 1 through 3, the investigator should apply clinical judgment to determine the need for reporting this as an AE or SAE and the need for any appropriate referral.

The C-SSRS will be collected at every visit.

8.2.2 *Vital Signs*

Blood pressure will be measured sitting, after at least 5 min at rest. The three measurements should be recorded 1 to 2 min apart, and the results averaged to inform eligibility at screening and baseline. Blood pressure, body temperature, and pulse rate will be obtained at screening, baseline, and day 2.

8.2.3 *Electrocardiogram*

Standard 12-lead ECGs will be obtained at screening, baseline, and day 2.

8.2.4 *Clinical Laboratory Tests*

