13.5.2.2 *Electrocardiogram Data*

ECG data and changes from baseline/screening will be summarised by visit. Frequency tabulations of the abnormalities will be provided, as well a summary using the ICH E14 Guideline: The Clinical Evaluation of QT/QTc Interval Prolongation and Proarrhythmic Potential for Non-Antiarrhythmic Drugs. ECG variables to be analysed will include heart rate (bpm), PR interval (ms), QRS interval (ms), QT interval (ms), and corrected QT interval using the following correction methods: QT corrected according to Bazett's formula [QTcB (ms)] and QT corrected according to Fridericia's formula [QTcF (ms)].

13.5.2.3 *Vital Signs*

Vital signs data and changes from baseline/screening will be summarised by visit. Frequency tabulations of the abnormalities will be provided. Vital sign variables to be analysed will include blood pressure [systolic (mmHg) and diastolic (mmHg)], body temperature (°C), and pulse rate (beats/min). The percentage of participants with values outside clinically important limits will be summarised, using the following limits:

Vital sign	Lower Limit	Upper Limit
Systolic blood pressure (mmHg)	90 mmHg	160 mmHg
Diastolic blood pressure (mmHg)	50 mmHg	100 mmHg
Pulse rate (bpm)	50 bpm	100 bpm
Body temperature (degrees Celsius)	-	37.5 °C

13.5.2.4 *Laboratory Data*

Observed values and changes from baseline for haematology and blood chemistry parameters will be summarised by visit. All presentations will be based on the International System of Units. The frequency of laboratory abnormalities will be tabulated.

By-participant data listings will flag laboratory values that are outside normal reference ranges or markedly abnormal findings.

13.5.2.5 *Columbia-Suicide Severity Rating Scale*

C-SSRS data, including item scores, suicidal ideation, and suicidal behaviour, will be summarised by visit.

13.5.3 *Participant Disposition, Demographic and Baseline Characteristics*

Participant disposition, including number of screen failures, participants in each analysis set, completers and early discontinuation as well as reason, will be summarised.

Demographic data and baseline characteristics, including age at screening, gender, race, ethnicity, height, body weight, BMI and duration of PTSD will be summarised.

13.5.4 *Medical History*

Medical history will be coded using MedDRA latest version and summarised and listed for all participants.

13.5.5 *Prior and Concomitant Medication*

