Primary Endpoint(s): The safety and tolerability endpoints include:

- AEs
- 12-lead ECGs
- Clinical laboratory tests
- Vital signs
- Suicidality measured via the C-SSRS
- BPRS+

Secondary Endpoint(s): Secondary Endpoint(s)

- Change in CAPS-5 total score from baseline
- Change in PCL-5 total score from baseline
- Change in SDS total score from baseline
- Change in EQ-5D-5L total score from baseline
- Proportion of participants with response (defined as a ≥ 15 point improvement on the CAPS-5 total score from baseline)
- Proportion of participants with remission (defined as CAPS-5 total score ≤ 20)

Additional Endpoint(s):

Additional Endpoint(s)

- Change in PACT total score from baseline
- Change in RAS total score from baseline
- 5D-ASC on day 1
- Summary of the Emotional Breakthrough Inventory (EBI) total score on day 2
- Participant acceptability of the treatment assessed via a semi-structured qualitative interview *
- Quantitative and descriptive characterisation of changes in the participant narrative as a result of treatment *
- Measures derived from the Cue app installed on the participant's smart phone *
- Changes in blood biomarkers after COMP360 therapy, as well as any relationship between biomarkers pre- and post-treatment, and clinical outcomes*

- Brain activation during fMRI tasks relating to trauma-related events and an emotional go/no-go task *

*Data from the semi-structured qualitative interview and data generated from the Cue app and the MRI and blood biomarker components of study will be assessed outside of the Clinical Study Report (CSR)

Estimand Framework

An estimand framework will not be used for this study since it is a descriptive, exploratory study.

Sample Size Determination

No formal sample size calculation has been performed for this exploratory study.

Analysis Sets

The Screening Analysis Set will consist of all participants who signed the ICF.

The Safety Analysis Set will consist of all participants who receive study drug.

The Full Analysis Set (FAS) will consist of all participants in the Safety Analysis Set who have at least one post-baseline efficacy assessment.

Hypothesis

There are no formal hypotheses being tested in this study.

Primary Endpoint Analyses

Safety will be evaluated based on AEs, ECG findings, clinical laboratory assessments, vital signs, BPRS+, and suicidality (as measured via the C-SSRS).

Secondary Endpoint Analyses

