7 GENERAL CONSIDERATIONS

All TFLs will be created using SAS® version 9.4 or later.

Listings will be sorted in the following order: participant, visit, and parameter unless otherwise stated. All data will be listed.

Unless otherwise specified, “baseline” is defined as the last observed value of the parameter of interest prior to dosing. This includes values collected at both scheduled and unscheduled visits. For numerical variables, change from baseline will be calculated as the difference between the value of interest and the corresponding baseline value.

Continuous data will be summarised descriptively using n (number of observations), mean, standard deviation (SD), median, minimum, and maximum.

Categorical data will be summarised using frequency counts and percentages. The denominator for a percentage will be the total number of participants in the relevant treatment group or analysis set (N), unless otherwise specified (on some occasions, percentages may be calculated using the total number of participants with available data at a particular visit or time point as the denominator [n]).

Unscheduled visits and retests (same visit number assigned) will not be displayed in by-visit summary tables but will be included in the data listings.

All individual participant data will be listed. Listings will include scheduled, unscheduled, retest and early discontinuation data.

All medical histories, adverse events (AEs), and prior and concomitant non-drug therapy will be coded from the actual verbatim term using the Medical Dictionary for Regulatory Activities (MedDRA) version 26.1 or later.

All prior and concomitant medications will be coded using the World Health Organization (WHO) Drug Global Dictionary (Sep-2023 version or later).

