8.3.5 Columbia-Suicide Severity Rating Scale (C-SSRS)

The following outcomes are C-SSRS categories and have binary responses (yes / no)⁶:

Table 9: C-SSRS Categories

Category	Question
Category 1	Wish to be Dead
Category 2	Non-Specific Active Suicidal Thoughts

Category 3	Active Suicidal Ideation with Any Methods (Not Plan) without Intent to Act
Category 4	Active Suicidal Ideation with Some Intent to Act, without Specific Plan
Category 5	Active Suicidal Ideation with Specific Plan and Intent
Category 6	Actual Attempt
Category 7	Has Subject Engaged in Non-suicidal Self-injurious Behaviour?
Category 8	Interrupted Attempt
Category 9	Aborted Attempt
Category 10	Preparatory Acts or Behaviour
Category 11	Suicidal Behaviour
Category 12	Suicide

The C-SSRS ‘past 12 months’ and ‘lifetime’ versions will be used at Screening, and subsequently the ‘since last visit’ version of the C-SSRS will be used at every other clinic visit.

There will be no imputation of missing data for the C-SSRS.

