14.3.1.10	MedDRA Summary of Treatment-Emergent Adverse Events of Special Interest (AESIs) by AESI Term, Preferred Term, Time of Onset and Duration of Adverse Event – Safety Analysis Set	IProg	14.3.1.6
14.3.1.11	MedDRA Summary of Treatment-Emergent Adverse Events (TEAEs) Leading to Study Withdrawal by Primary System Organ Class and Preferred Term – Safety Analysis Set	IProg	14.3.1.2
14.3.1.12	MedDRA Summary of Treatment-Emergent Adverse Events (TEAEs) Occurring Within 24 Hours of Study Drug Administration by Primary System Organ Class, Preferred Term, and Start/Stop Time Since Study Drug Administration – Safety Analysis Set	IProg	
14.3.1.13	MedDRA Summary of Treatment-Emergent Adverse Events of Special Interest (AESIs) Occurring Within 24 Hours of Study Drug Administration by AESI Term, Preferred Term, and Start/Stop Time Since Study Drug Administration – Safety Analysis Set	IProg	14.3.1.12
14.3.1.14	MedDRA Summary of Pre-Treatment Adverse Events (Aes) by Primary System Organ Class, and Preferred Term – Screening Analysis Set	IProg	14.3.1.2
14.3.4	Laboratory Values		
14.3.4.1	Summary Statistics of Observed Values and Change from Baseline in Haematology – Safety Analysis Set	IProg	
14.3.4.2	Summary Statistics of Observed Values and Change from Baseline in Chemistry – Safety Analysis Set	IProg	14.3.4.1
14.3.4.3	Normal Range Shifts from Baseline in Haematology Values – Safety Analysis Set	IProg	
14.3.4.4	Normal Range Shifts from Baseline in Chemistry Values – Safety Analysis Set	IProg	14.3.4.3

Table Number	Table Title	Validation Method	Shell Number (if Repeat)
14.3.5	Vital Signs	IProg	
14.3.5.1	Summary Statistics of Observed Values and Change from Baseline in Vital Signs by Visit and Timepoint – Safety Analysis Set	IProg	
14.3.5.2	Overall Summary of Clinically Important Vital Signs Values – Safety Analysis Set	IProg	
14.3.6	Other Safety		
14.3.6.1	Summary Statistics of Observed Values and Changes from Baseline to Day 2 in ECG Variables – Safety Analysis Set	IProg	14.3.4.1
14.3.6.2	ECG Clinical Interpretation – Shift from Baseline to Day 2 – Safety Analysis Set	IProg	
14.3.6.3	Summary of QTc Interval Categories – Safety Analysis Set	IProg	
14.3.6.4	Summary of C-SSRS by Visit – Safety Analysis Set	IProg	
14.3.6.5	Summary of BPRS+ Total Score by Visit – Safety Analysis Set	IProg	
14.3.6.6	Summary of BPRS+ Symptom Score by Visit – Safety Analysis Set	IProg	

Figure Number	Figure Title	Validation Method	Shell Number (if Repeat)
14.2	Efficacy Endpoints		

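### The C-SSRS, a primary safety endpoint, is tabulated only visit by visit, so no C-SSRS-based count of participants with new or worsened suicidality after dosing is planned

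*SAP*

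**What the plan says.** The SAP synopsis and SAP Table 1 list "Suicidality measured via the C-SSRS" among the primary safety and tolerability endpoints, as does protocol section 3.1.

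The planned analysis is short. Protocol section 13.5.2.5 says "C-SSRS data, including item scores, suicidal ideation, and suicidal behaviour, will be summarised by visit". SAP section 10.5 says "C-SSRS data will be summarised by visit" (Table 14.3.6.4) and adds Listing 16.2.9.2. The only C-SSRS table in SAP section 16 is titled "Summary of C-SSRS by Visit". SAP section 8.3.5 defines twelve yes/no categories and derives nothing from them: no highest post-dose category, no any-time-post-dose flag, no new-onset or worsening flag. The post-lock addendum adds nothing for the C-SSRS.

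On timing, protocol section 8.2.1 says "The C-SSRS will be collected at every visit". After screening, SAP section 8.3.5 says the since-last-visit "version of the C-SSRS will be used at every other clinic visit". SAP section 7 adds that "Unscheduled visits and retests (same visit number assigned) will not be displayed in by-visit summary tables"; they are listed only.

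Suicidality also enters through adverse events. SAP Table 5 has AESI terms for suicidal behaviour and suicidal ideation, and Table 14.3.1.9 gives participant and event counts for treatment-emergent AESIs. Protocol section 8.2.1 makes a yes on ideation questions 4 or 5, or on any behaviour item, reportable as an AE or SAE. For questions 1 to 3 it leaves reporting to the investigator's judgment.

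**The concern.** For a single-dose, single-arm safety study, a natural question for this endpoint is how many participants had ideation or behaviour after dosing that was absent, or milder, before. Each since-last-visit form covers its own interval, so each row of the by-visit table is a separate snapshot. The table cannot show whether positives in different rows are one person or several, or whether a positive is new relative to that person's pre-dose status. Scattered events can look uniformly rare. Laboratory and ECG data, also primary endpoints, get shift tables (SAP sections 10.2 and 10.4); the C-SSRS does not.

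The part at stake is low-level ideation. Protocol section 6.3 excludes ideation items 4-5 and suicidal behaviour within the past year, so participants should enter with no ideation or with items 1-3. New onset or worsening within items 1-3 is the range in which adverse event reporting is discretionary.

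**Working it through.** The documents give no suicidality rate or target, so there is no figure to reproduce. The check asks what the planned outputs can determine.

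**Inputs**
- N = 20: SAP section 4.6 expects approximately 20; the protocol says up to 20.
- V = 8 scheduled post-dose C-SSRS assessments: Day 1 (end of session), Day 2, and Weeks 1, 2, 4, 6, 9 and 12 (schedules in protocol section 5.3 and SAP section 4.3).
- Per-visit counts: assumed. All rows are taken as complete, so each denominator is 20.

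**Step 1: what by-visit counts determine.** If c participants are positive at each of the 8 visits, the number ever positive lies between c (always the same people) and min(N, 8c) (always different people).
- c = 1: from 1/20 = 5% (exact 95% CI 0.1% to 24.9%) to min(20, 8) = 8/20 = 40% (19.1% to 63.9%).
- c = 2: from 2/20 = 10% (1.2% to 31.7%) to min(20, 16) = 16/20 = 80% (56.3% to 94.3%).

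The same table therefore fits very different participant-level results.

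**Step 2: a specific illustration.** Suppose 4 participants are each positive once, at four different visits, at items 1-3, and none is reported as an adverse event.
- Largest row: 1/20 = 5%.
- Participants ever positive: 4/20 = 20%.
- Exact (Clopper-Pearson) interval for x = 4, n = 20: lower limit = Beta quantile(0.025; x, n - x + 1) = Beta(0.025; 4, 17) = 5.7%; upper limit = Beta quantile(0.975; x + 1, n - x) = Beta(0.975; 5, 16) = 43.7%.

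**Step 3: which planned output counts whom, by type of post-dose finding**

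| C-SSRS finding | By-visit table | Participant count in AESI table |
|---|---|---|
| Ideation items 4-5 | Yes, if at a scheduled visit | Yes, through mandatory AE reporting |
| Any behaviour item | Yes, if at a scheduled visit | Yes, through mandatory AE reporting |
| New or worse ideation, items 1-3 | Yes, if at a scheduled visit | Only if the investigator judges it an AE |

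The last row is the gap. The AESI behaviour term also includes intentional self-injury, whereas the C-SSRS records non-suicidal self-injury separately (Category 7), so that AESI total can mix the two.

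**Step 4: the pre-dose reference.** SAP Table 17 sets the safety baseline at Day -1. With weekly screening-period visits, the since-last-visit form that day looks back only a short time. The screening form looks back 12 months (and over the lifetime, per SAP section 8.3.5). Pooling the screening-period and baseline since-last-visit forms covers about 3 to 6 weeks (protocol section 7.2.2), against 12 weeks of follow-up. The post-dose window is thus 12/6 = 2 to 12/3 = 4 times as long.

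**The case against.** A reader might infer from section 10.5 that the plan gives no participant count of post-dose suicidality at all. The documents do not support that. Table 14.3.1.9 counts participants with treatment-emergent suicidal ideation or behaviour over the whole post-dose period, Table 14.3.1.10 adds onset and duration, and the treatment-emergent definition in SAP section 8.3.1 covers worsening as well as new onset. The more severe C-SSRS findings must be reported and so should reach those tables. This part of the objection stands, and it confines the gap to items 1-3 and to the lack of a cross-check.

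A reader might also infer that the data cannot answer the question. They can: Listing 16.2.9.2 is sorted by participant and visit, includes unscheduled assessments, and can be counted by hand for about 20 people. But no rule fixes the pre-dose reference or what counts as worse, so two readers could reach different counts.

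Third, the study is descriptive, has no hypotheses, and its SAP follows the protocol's by-visit wording. That is true: the documents are not in contradiction here. The point is that the summary is thin for a primary endpoint.

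Finally, the 4-of-20 example is constructed. It misleads only if all four findings are at items 1-3 and none is reported as an adverse event. That condition is part of the illustration.

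**Conclusion.** The point holds in a limited form. No planned table gives a C-SSRS-based, participant-level count of new or worsened suicidality after dosing, and unscheduled assessments are left out of the one C-SSRS table. Through the AESI tables, the plan does count suicidality reported as adverse events. What remains uncounted is new or worse item 1-3 ideation that the investigator does not report, and nothing derived from the C-SSRS is available to check the AESI count.

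The size cannot be estimated from the documents. In the assumed illustration it is 5% at most in any row against 20% overall; one positive per visit over 8 visits is compatible with anything from 5% to 40% of participants.

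This rests on two assumptions. The AE-reporting rule in protocol section 8.2.1 must still apply in protocol V5.0, which the SAP cites; the supplied protocol may be a different version, since it lacks the BPRS+ and the added AESI terms. And the shell for Table 14.3.6.4, which is not in the documents, must match its title and contain no any-time-post-dose row.

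**What to change.** Keep the by-visit table and add one participant-level C-SSRS table on the Safety Analysis Set, including unscheduled assessments:

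- **Ideation:** highest category pre-dose (none, 1 to 5) against highest category at any post-dose assessment, with the number of participants with new or worsened ideation.
- **Suicidal behaviour:** number of participants with any post-dose Category 6, 8, 9, 10, 11 or 12, by pre-dose status. List these explicitly and do not rank them: apart from ideation (1 to 5), the numbering in SAP Table 9 is not a severity order.
- **Non-suicidal self-injury (Category 7):** shown separately.
- **Pre-dose reference:** the screening-period and baseline since-last-visit assessments, with the 12-month screening result alongside because the pre-dose window is shorter than follow-up. State that the Day 1 end-of-session form counts as post-dose, although its look-back starts at the previous visit.
- **Reconciliation:** compare the counts with the suicidal ideation and suicidal behaviour rows of Table 14.3.1.9 and explain differences.

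The cost is one extra table from data already collected. The existing addendum was written after database lock and added a comparable summary for the mDESS, so this one could be added the same way, labelled as post-lock. The drawback is some upward bias in the new-onset counts from the shorter pre-dose window, which the 12-month result makes visible but does not remove. The AE-reporting rule itself is unaffected.
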